14.0 STATISTICAL CONSIDERATIONS

A maximum of 48 patients will be enrolled in this Phase II study. Cohort 1 will enroll up to 24 CLL patients who are refractory to or have relapsed after at least one prior therapy; cohort 2 will enroll up to 24 untreated CLL patients with high-risk molecular features such as del(17p), mutated *TP53*, del(11q), unmutated *IGHV* gene, or are >65 years of age. The primary objective is to evaluate overall response (OR) during the first 6 months of therapy. The primary efficacy endpoint, overall response (OR), is defined as CR, CRi or PR that occurs during the first 6 months of therapy.

EFFICACY

For cohort 1, the target overall response rate is 30%. The Bayesian approach of Thall, Simon, Estey will be implemented for the futility monitoring.³¹ The following futility stopping rule will be applied in cohort size of 3, starting from the 9th patient: $\text{prob}\{p(\text{OR}) > 0.3\} < 0.05$, where $p(\text{OR})$ denotes the overall response rate. That is, the trial will be stopped early due to futility, if during the study we determine that there is less than 5% chance that the OR is more than 30%. Assuming that the prior distribution of $p(\text{OR})$ is beta (0.6, 1.4), the stopping boundaries corresponding to this futility monitoring rule are shown below in Table 14.1. The operating characteristics (OCs) for this futility stopping rule are summarized in Table 14.2.

Table 14.1. Futility stopping boundaries for cohort 1, in cohort size of 3.

Number of patients	Stop the trial if there are this many patients achieving OR
9	0

12-15	0-1
18	0-2
21	0-3

Table 14.2. Operating characteristics for the monitoring of OR rate in cohort 1.

True OR Rate	Early Stopping Probability	Average number of patients treated
0.1	0.88	13.8
0.2	0.45	19.4
0.3	0.14	22.6
0.4	0.03	23.7
0.5	0.005	23.9

For cohort 2, the OR rate is ~30% with Rituximab and we target to reach an OR rate of 50% with the combination therapy. The same Bayesian approach of Thall, Simon, Estey will be implemented for the futility monitoring.³¹ The following futility stopping rule will be applied in cohort size of 3, starting from the 9th patient: $\text{prob}\{p(\text{OR}) > 0.3 + \delta\} < 0.05$, where $p(\text{OR})$ denotes the response rate and $\delta = 0.2$. That is, the trial will be stopped early due to futility, if during the study we determine that there is less than 5% chance that the OR rate with the combination therapy will improve from 30% (Rituximab alone) to 50%. Assuming that the prior distribution of $p(\text{OR})$ is beta (0.6, 1.4), the stopping boundaries corresponding to this futility monitoring rule are shown below in Table 14.3. The operating characteristics (OCs) for this futility stopping rule are summarized in Table 14.4.

Table 14.3. Futility stopping boundaries, in cohort size of 3, for cohort 2.

Number of patients	Stop the trial if there are this many patients achieving OR
9	0-2
12	0-3
15	0-4
18	0-5
21	0-7

Table 14.4. Operating characteristics for monitoring of OR rate in cohort 2.

True OR Rate	Early Stopping Probability	Average number of patients treated
0.2	0.97	11.0
0.3	0.78	14.8
0.4	0.44	19.1
0.5	0.16	22.2

0.6	0.04	23.5
0.7	0.005	23.9

TOXICITY

The Bayesian approach of Thall, Simon, Estey will be implemented for toxicity monitoring for patients enrolled in cohorts 1 and 2, where toxicity is defined as any grade 3 or higher non-hematological toxicity which is at least possibly related to the treatment.³¹ The toxicity, denoted as TOX will be monitored by the Bayesian stopping boundaries calculated based on beta-binomial distributions. We assume as a priori, $p(\text{TOX}) \sim \text{beta}(0.6, 1.4)$. The study will be stopped for toxicity if $\Pr(p(\text{TOX}) > 0.30 \mid \text{data}) > 0.92$. That is, we will stop the trial for new patient enrollment if at any time during the study we determine that there is more than 92% chance that the toxicity rate is more than 30%. The toxicity monitoring rule will be applied starting from the 6th patient, and then in cohort size of 6. The toxicity will be considered continuously throughout the study treatment duration. Stopping boundaries corresponding to this toxicity monitoring rule are shown in Table 14.5 below. The operating characteristics for toxicity monitoring are summarized in Table 14.6.

Table 14.5. Toxicity stopping boundaries in cohort size of 6 for patients enrolled in cohorts 1 and 2.

Number of patients	Stop the trial if there are this many patients having toxicity
6	4-6
12	7-12
18	9-18
24	11-24
30	13-30
36	15-36
42	18-42

Table 14.6. Operating characteristics for toxicity monitoring.

True Toxicity Rate	Early Stopping Probability	Average number of patients treated
0.1	0.001	47.9
0.2	0.02	47.1
0.3	0.19	42.3
0.4	0.61	30.5
0.5	0.93	18.2

ANALYSIS PLAN

Summary statistics will be provided for continuous variables. Frequency tables will be used to summarize categorical variables. The overall response (OR) rate will be estimated along with

the 95% credible interval.

Data from all patients who receive any study drug will be included in the safety analyses. Patients who entered the study and did not take any of the study drugs and had this confirmed will not be evaluated for safety. The severity of the toxicities will be graded according to the NCI CTCAE v4.0 whenever possible. We will follow standard reporting guidelines for adverse events. Safety data will be summarized by category, severity and frequency. The proportion of patients with AEs will be estimated, along with the Bayesian 95% credible interval. Kaplan-Meier method will be used to assess the overall survival (OS) and progression-free survival (PFS) probabilities. The change of biomarkers over time will be assessed through fitting linear or non-linear mixed effect models.

This study will be conducted as described in this protocol, except for an emergency situation in which the protection, safety, and wellbeing of the patient requires immediate intervention, based on the judgment of the investigator or his/her designee. In the event of a significant deviation from the protocol, the investigator will notify the MDACC surveillance committee following the institutional guidelines.

Statistical Language for the correlative studies: Descriptive statistics including plots, mean, median and standard deviations will be used to summarize data. For continuous outcomes, t-test and ANOVA will be used to compare outcome measures across patient characteristics. Dunnett's and Tukey's test that properly adjust for multiplicity in multiple tests will be implemented. Pair-wise comparisons will be performed using pre- and post-therapy samples from each patient. The chi-square (c2) test or Fisher's exact test will be used to test the association between two categorical variables such as disease state and performance status. Both univariate and multivariate logistic regressions will be performed to model prognostic factors.

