This study will enroll 48 patients into two cohorts. Cohort 1 will enroll up to 24 CLL patients who are refractory to or have relapsed after at least one prior therapy; cohort 2 will enroll up to 24 untreated CLL patients with high-risk molecular features such as del(17p), mutated TP53, del(11q), unmutated IGHV gene, or are >65 years of age

Is this an NCI-Cancer Therapy Evaluation Protocol (CTEP)? No

Is this an NCI-Division of Cancer Prevention Protocol (DCP)? No

Statistical Considerations:

A maximum of 48 patients will be enrolled in this Phase II study. Cohort 1 will enroll up to 24 CLL patients who are refractory to or have relapsed after at least one prior therapy; cohort 2 will enroll up to 24 untreated CLL patients with high-risk molecular features such as del(17p), mutated TP53, del(11q), unmutated IGHV gene, or are >65 years of age. The primary objective is to evaluate overall response (OR) during the first 6 months of therapy. The primary efficacy endpoint, overall response (OR), is defined as CR, CRi or PR that occurs during the first 6 months of therapy.

EFFICACY

For cohort 1, the target overall response rate is 30%. The Bayesian approach of Thall, Simon, Estey will be implemented for the futility monitoring. The following futility stopping rule will be applied in cohort size of 3, starting from the 9th patient: $\text{prob}\{p(\text{OR}) > 0.3\} < 0.05$, where $p(\text{OR})$ denotes the overall response rate. That is, the trial will be stopped early due to futility, if during the study we determine that there is less than 5% chance that the OR is more than 30%. Assuming that the prior distribution of $p(\text{OR})$ is beta (0.6, 1.4), the stopping boundaries corresponding to this futility monitoring rule are shown below in Table 14.1. The operating characteristics (OCs) for this futility stopping rule are summarized in Table 14.2.

Table 14.1. Futility stopping boundaries for cohort 1, in cohort size of 3.

Number of patients	Stop the trial if there are this many patients achieving OR
9	0
12-15	0-1
18	0-2
21	0-3

Table 14.2. Operating characteristics for the monitoring of OR rate in cohort 1.

True OR Rate	Early Stopping Probability	Average number of patients treated
0.1	0.88	13.8
0.2	0.45	19.4
0.3	0.14	22.6
0.4	0.03	23.7
0.5	0.005	23.9

For cohort 2, the OR rate is ~30% with Rituximab and we target to reach an OR rate of 50%

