4.0 TREATMENT PLAN

4.1 Study Design

This is a phase II open label single-arm study to evaluate combined lirilumab and rituximab in patients with CLL.

	C1D1	C1D8 (±2 days)	C1D15 (±2 days)	C1D22 (±2 days)	C2-C12 D1 (±7 days)	C13-C24 D1 (±7 days)
Rituximab	375 mg/m ²	375 mg/m ²	375 mg/m ²	375 mg/m ²	375 mg/m ²	–
Lirilumab	3 mg/kg	–	–	–	3 mg/kg	3 mg/kg

Each cycle is 4 weeks. Patients will receive rituximab (375 mg/m² IV) weekly for the first 4 weeks (Days 1, 8, 15, 22), and then with the start of each course. Lirilumab (3 mg/kg IV) will be given on day 1 of each cycle. Rituximab will be given for the first 12 cycles and lirilumab will continue for up to 24 cycles.

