6.0 DOSE DELAYS AND MODIFICATIONS

Patients who experience Grade 3 or 4 toxicity that can be clearly attributed to either lirilumab or to rituximab may continue treatment with the other agent while the causative agent is delayed until resolution of toxicity to grade ≤ 1 or baseline. In cases where Grade 3 or 4 toxicity cannot be attributed to a specific study drug, both study drugs should be held regardless of attribution of toxicity until the toxicity is resolved to grade ≤ 1 or baseline.

Rituximab and lirilumab administration should be delayed and increased monitoring of patients should ensue if any of the following drug-related adverse event(s) occurs:

- Any Grade ≥ 2 ALT, AST, or total bilirubin
- Any Grade ≥ 2 non laboratory non-skin drug related adverse event except for fatigue
- Any Grade ≥ 2 endocrine drug-related adverse event
- Any Grade ≥ 3 skin drug related adverse event
- Any Grade ≥ 3 drug-related laboratory abnormality (except lymphopenia or any electrolyte abnormality without any clinical sequelae that is either spontaneously reversible or resolves with clinical management to grade 2 or less within 72 hours)
- Any AE, laboratory abnormality or inter-current illness, which in the judgment of the investigator, warrants delaying the dose of study medication

Discontinuation of lirilumab will occur in the following situations:

- AST, ALT, or T Bili \geq Grade 3
- Grade 2 AST or ALT and symptomatic liver inflammation (e.g., right upper quadrant tenderness, jaundice)
- AST or ALT $> 3 \times$ ULN and concurrent total bilirubin $> 2 \times$ ULN in the absence of evidence of cholestasis (Hy's law)

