1. CBC, platelet count and differential, sodium, potassium, calcium, BUN, creatinine, glucose, phosphorous, magnesium, albumin, total protein, alkaline phosphatase, total bilirubin, ALT, AST, uric acid, LDH

Cycle 3 Day 1 (Rituximab and Lirilumab) (+/- 1 week)

1. CBC, platelet count and differential, sodium, potassium, calcium, BUN, creatinine, glucose, phosphorous, magnesium, albumin, total protein, alkaline phosphatase, total bilirubin, ALT, AST, uric acid, LDH, serum immunoglobulins, TSH, Free T4
2. B, T, NK cell counts and subset analyses on the peripheral blood
3. Serum or urine β -hCG pregnancy test (for women of childbearing potential)
4. Vital signs, history and physical examination

Cycle 3 Day 15 (no mAb) (+/- 3 day)

1. CBC, platelet count and differential, sodium, potassium, calcium, BUN, creatinine, glucose, phosphorous, magnesium, albumin, total protein, alkaline phosphatase, total bilirubin, ALT, AST, uric acid, LDH
2. Vital signs, history and physical examination

End of Cycle 3 (response assessment) (+/- 1 week)

1. CBC, platelet count and differential, sodium, potassium, calcium, BUN, creatinine, glucose, phosphorous, magnesium, albumin, total protein, alkaline phosphatase, total bilirubin, ALT, AST, uric acid, LDH, β -2 microglobulin, serum immunoglobulins
2. Vital signs, History and Physical Examination
3. B, T, NK cell counts and subset analyses on the peripheral blood
4. TSH, Free T4
5. Serum or urine β -hCG pregnancy test (for women of childbearing potential)
6. Bone marrow aspiration and biopsy with multi-color flow cytometry for MRD evaluation
7. CT scan of the neck (if indicated), chest, abdomen, and pelvis with IV and oral contrast. PET scan may be used instead of the CT scan imaging.

Cycle 4 Day 1 (Rituximab and Lirilumab) (+/- 1 week)

1. CBC, platelet count and differential, sodium, potassium, calcium, BUN, creatinine, glucose, phosphorous, magnesium, albumin, total protein, alkaline phosphatase, total bilirubin, ALT, AST, uric acid, LDH
2. Serum or urine β -hCG pregnancy test (for women of childbearing potential)
3. Vital signs, history and physical examination

Cycle 4 Day 15 (no mAb) (+/- 3 day)

1. CBC, platelet count and differential, sodium, potassium, calcium, BUN, creatinine, glucose, phosphorous, magnesium, albumin, total protein, alkaline phosphatase, total bilirubin, ALT, AST, uric acid, LDH
2. Vital signs, history and physical examination

Cycle 5 Day 1 (Rituximab and Lirilumab) (+/- 1 week)

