1. CBC, platelet count and differential, sodium, potassium, calcium, BUN, creatinine, glucose, phosphorous, magnesium, albumin, total protein, alkaline phosphatase, total bilirubin, ALT, AST, uric acid, LDH, serum immunoglobulins, TSH, Free T4
2. B, T, NK cell counts and subset analyses on the peripheral blood
3. Serum or urine β -hCG pregnancy test (for women of childbearing potential)
4. Vital signs, history and physical examination

Cycle 5 Day 15 (no mAb) (+/- 3 day)

1. CBC, platelet count and differential, sodium, potassium, calcium, BUN, creatinine, glucose, phosphorous, magnesium, albumin, total protein, alkaline phosphatase, total bilirubin, ALT, AST, uric acid, LDH
2. Vital signs, history and physical examination

Cycle 6 Day 1 (Rituximab and Lirilumab) (+/- 1 week)

1. CBC, platelet count and differential, sodium, potassium, calcium, BUN, creatinine, glucose, phosphorous, magnesium, albumin, total protein, alkaline phosphatase, total bilirubin, ALT, AST, uric acid, LDH, serum immunoglobulins, TSH, Free T4
2. B, T, NK cell counts and subset analyses on the peripheral blood
3. Serum or urine β -hCG pregnancy test (for women of childbearing potential)
4. Vital signs, history and physical examination

Cycle 6 Day 15 (no mAb) (+/- 3 day)

1. CBC, platelet count and differential, sodium, potassium, calcium, BUN, creatinine, glucose, phosphorous, magnesium, albumin, total protein, alkaline phosphatase, total bilirubin, ALT, AST, uric acid, LDH
2. Vital signs, history and physical examination

End of Cycle 6 (response assessment) (+/- 1 week)

1. CBC, platelet count and differential, sodium, potassium, calcium, BUN, creatinine, glucose, phosphorous, magnesium, albumin, total protein, alkaline phosphatase, total bilirubin, ALT, AST, uric acid, LDH, β -2 microglobulin, serum immunoglobulins
2. Vital signs, History and Physical Examination
3. B, T, NK cell counts and subset analyses on the peripheral blood
4. TSH, Free T4
5. Serum or urine β -hCG pregnancy test (for women of childbearing potential)
6. Bone marrow aspiration and biopsy with multi-color flow cytometry for MRD evaluation
7. CT scan of the neck (if indicated), chest, abdomen, and pelvis with IV and oral contrast. PET scan may be used instead of the CT scan imaging.

Cycle 7 onwards (All evaluations can be +/- 1 week) (Rituximab on day 1 of cycles 7-12; Lirilumab on day 1 of cycles 7-24)

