1. CBC, platelet count and differential; serum sodium, potassium, calcium, BUN, creatinine, glucose, phosphorous, magnesium, albumin, total protein, alkaline phosphatase, total bilirubin, ALT, AST, uric acid, LDH at least monthly.
2. Complete history and physical examination including vital signs at least monthly.
3. Quantitative immunoglobulin levels every month
4. B, T, NK cell counts and subset analyses on the peripheral blood every 3 months
5. TSH, Free T4 every 3 months
6. Serum or urine β -hCG pregnancy test (for women of childbearing potential) before dose of lirilumab
7. Urinalysis every 3 months
8. Bone marrow aspiration and biopsy with multi-color flow cytometry for MRD evaluation every 3 months
9. CT scan of the neck (if indicated), chest, abdomen, and pelvis with IV and oral contrast every 3 months. PET scan may be used instead of the CT scan imaging.

End of Study Visit – Patients, who are taken off study for any reason, will have an end of study visit. The end of study visit will occur 30 days (+/- 1 week) after the last dose of the study drugs. At this visit, the patient will have labs (CBC, platelet count and differential, sodium, potassium, calcium, BUN, creatinine, glucose, phosphorous, magnesium, albumin, total protein, alkaline phosphatase, total bilirubin, ALT, AST, uric acid, LDH), history and physical examination, serum immunoglobulins, B, T, NK cell counts and subset analyses on the peripheral blood, bone marrow aspiration and biopsy with multi-color flow cytometry for MRD evaluation (if the previous bone marrow evaluation was >3 months ago), and CT or PET imaging (if the previous CT or PET imaging was >3 months ago).

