12.0 DISCONTINUATION OF STUDY TREATMENT

A patient's treatment with study drugs may be discontinued for any of the following reasons:

- Clinically significant progressive disease
- Adverse events that are not manageable with dose adjustments and/or optimal medical management, or that, in the opinion of the investigator, pose an unacceptable risk for the patient.
- Investigator decision
- Patient decision (e.g., withdrawal of consent)
- Study termination by Sponsor

Patients who experience toxicity that can be clearly attributed to either lirilumab or rituximab may continue treatment with the other agent. If toxicity cannot be clearly attributed to a single agent, treatment with both agents should be discontinued. Patients who discontinue treatment for reasons other than progressive disease should remain on study and continue to have disease assessments per protocol.

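### Would a response first documented at a delayed end-of-cycle-6 work-up fall outside the 6-month primary endpoint?

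*Combined protocol and SAP*

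**What the plan says.** The abstract and Section 14.0 give the same time frame: "The primary objective is to evaluate overall response (OR) during the first 6 months of therapy". The endpoint, overall response, "is defined as CR, CRi or PR that occurs during the first 6 months of therapy". Neither place gives a day count or names a visit.

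Section 9.0 fixes the full work-ups (marrow plus CT or PET) by cycle: "End of Cycle 3 (response assessment) (+/- 1 week") and "End of Cycle 6 (response assessment) (+/- 1 week"). From cycle 7 the calendar takes over, with marrow and CT, the latter "with IV and oral contrast every 3 months".

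Two provisions can move dates. The table in Section 4.1 allows dosing at "C2-C12 D1 (±7 days"), without saying whether the window is counted from cycle 1 day 1 or from the previous dose. Section 6.0 says that when a Grade 3 or 4 toxicity cannot be assigned to one drug, "both study drugs should be held regardless of attribution of toxicity until the toxicity is resolved to grade" 1 or below, or to baseline. It states no maximum delay.

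Section 10.0 counts patients with missing or absent response assessments as non-responders and does not mention late ones. Under Section 12.0, patients who stop treatment for reasons other than progression "should remain on study and continue to have disease assessments per protocol".

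**The concern.** The endpoint runs on months and the assessments run on cycles. Only two full work-ups fall inside the endpoint period. If the second is done on, say, day 190 because earlier doses were late, a patient whose response is first documented there is a responder by cycle and a non-responder by calendar.

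The same count gives the primary estimate and drives the futility boundaries, in cohorts of at most 24. Dropping such patients would lower the response rate and make a futility stop more likely. Leaving the matter open could mean scoring the case after the result is known, in an open-label study with investigator-assessed response.

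**Working it through.** **Dates without toxicity holds** (Section 4.1: each cycle is 4 weeks; Section 9.0: visit window of 7 days either way)

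- End of cycle 6: 6 × 28 = day 168; latest with the visit window 168 + 7 = day 175.
- Six months: 365.25 / 2 = 182.6 days, taken as day 183. Calendar half-years run from 181 to 184 days.
- Slack: 183 − 168 = 15 days, or 183 − 175 = 8 days at the late edge of the visit window.
- Dosing windows anchored to cycle 1 day 1: 168 + 7 + 7 = day 182. This extreme sits at the limit.
- Dosing windows that roll from the previous dose: two late starts plus the visit window give 168 + 14 + 7 = day 189, and three late starts alone give 168 + 21 = day 189.

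A conflict therefore needs rolling windows used to the full several times, or holds that move the visit by more than 8 to 15 days.

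**How the protocol uses months.** Section 9.0 schedules marrow every 3 months from cycle 7. Section 13.0 collects marrow samples after C9, C12, C15 and so on to C24, which is every 3 cycles, or 3 × 28 = 84 days. The two schedules agree only if a month stands for a cycle. On that usage, 6 months of therapy is six cycles and its work-up is the end-of-cycle-6 assessment.

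**The plan's own figures.** With a beta(0.6, 1.4) prior, stop at n patients with x responders if Pr(p > p₀ | beta(0.6 + x, 1.4 + n − x)) < 0.05. At n = 9/12/15/18/21 this gives stopping at or below 0/1/1/2/3 for cohort 1 (p₀ = 0.3) and 2/3/4/5/7 for cohort 2 (p₀ = 0.5), as in Tables 14.1 and 14.3. Exact stopping probabilities at target are 0.139 (cohort 1, rate 0.30) and 0.160 (cohort 2, rate 0.50), against the stated 0.14 and 0.16.

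**Possible size.** The inputs below are assumptions, because the documents give none: a hold chance of 5% or 10% at each of the five starts of cycles 2 to 6, a hold of 7 or 14 days that moves the visit, and half of responses first documented at cycle 6.

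- 14-day holds, visit on its due day. One hold gives day 182, so two are needed. At 5%: 1 − 0.95⁵ − 5 × 0.05 × 0.95⁴ = 0.023. At 10%: 1 − 0.90⁵ − 5 × 0.10 × 0.90⁴ = 0.081.
- 14-day holds, visit spread evenly over 7 days either way: 0.104 and 0.213.
- 7-day holds with the same spread: 0.010 and about 0.037.
- Times 0.5, the share of responders lost is 1.1–4.1%, 5.2–10.7% and 0.5–1.8%. With 0.3 to 0.7 in place of 0.5, the two 14-day cases become 0.7–5.7% and 3.1–14.9%.

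In patients: a full cohort at target has 24 × 0.30 = 7.2 or 24 × 0.50 = 12 responders. A 4.1% loss is 7.2 × 0.041 = 0.30 or 12 × 0.041 = 0.49 of a patient. A 10.7% loss is 0.77 or 1.28 patients.

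Stopping probability at target rate × (1 − loss):

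| Loss | Cohort 1 | Cohort 2 |
|---|---|---|
| 0% | 0.139 | 0.160 |
| 1% | 0.145 | 0.170 |
| 3% | 0.157 | 0.191 |
| 5% | 0.170 | 0.214 |
| 10% | 0.206 | 0.279 |

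These increases are errors only if the cycle-6 definition is the intended one. Tables 14.2 and 14.4 are indexed by the response rate of the endpoint as defined. If late responses do not count, that rate is lower and the rule performs as tabulated.

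**The case for a change.** The best case for amending the plan is that the gap is real and cheap to close. No visible text equates the two clocks or scores a late work-up. Section 6.0 has broad triggers: both drugs are delayed for most related non-laboratory, non-skin events of Grade 2 or higher, and for Grade 2 or higher liver tests. A total shift of 8 to 15 days over five cycle starts is therefore plausible. At a futility look, one responder can decide whether a cohort continues, and a rule written beforehand removes discretion.

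The silence stands, and a clarifying clause would do no harm. The rest is weaker. Section 6.0 lets the other agent continue when a Grade 3 or 4 toxicity is clearly due to one drug, so the cycle clock need not move. The abstract cites an attached evaluation schedule that the public file does not show, so silence on how windows are anchored cannot be asserted firmly. The term used for the endpoint, occurrence, can mean onset rather than first documentation. Responses documented at cycle 3 are unaffected on any reading.

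Nor is the obvious amendment a clear gain. Counting whatever is found at the cycle-6 visit, on any date, leaves the period open-ended for delayed patients, because holds have no stated maximum. Early discontinuers have no cycle-6 visit and would need a separate limit. If that were day 168 ± 7, a response on days 176 to 183 that counts now would be lost. A single calendar limit treats everyone alike and is a legitimate choice.

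**Conclusion.** The concern does not call for a change. It is a missing detail that analysts would fill sensibly by taking the end-of-cycle-6 assessment as the 6-month assessment, in line with the protocol's own use of months for cycles. Followed on schedule, that work-up falls on day 168, at most day 175, or day 182 with anchored dosing windows. The stopping boundaries and probabilities in Tables 14.1 to 14.4 reproduce.

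The effect is confined to delayed patients whose response was not already documented at cycle 3. Its size cannot be derived from the documents and is probably small: 0.5% to 4.1% of responders in the milder scenarios above, under half a patient per cohort. The larger values need 14-day holds together with an even spread of visit dates over the whole window. All of them assume that holds move the visit and, in the central case, that half of responses first appear at cycle 6. The conclusion would be weaker if the cycle windows do roll forward and long holds turn out to be common.

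### The futility action for each cohort is written as stopping the trial, although Tables 14.1 to 14.4 hold only if each cohort closes on its own data

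*Combined protocol and SAP*

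**What the plan says.** In Section 14.0 (Efficacy) each futility rule opens by naming one cohort, and the tables that follow are titled for that cohort. The monitoring rule "will be applied in cohort size of 3, starting from the 9th patient", and each cohort enrols up to 24. Cohort 1 is judged against a 30% response rate. For cohort 2 the plan says: "For cohort 2, the OR rate is ~30% with Rituximab and we target to reach an OR rate of 50"%.

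The action is not limited in the same way. For cohort 1: "the trial will be stopped early due to futility, if during the study we determine that there is less than 5% chance" that the response rate exceeds 30%. For cohort 2: "That is, the trial will be stopped early due to futility", on the corresponding condition for 50%. The boundary columns of Tables 14.1 and 14.3 are both headed "Stop the trial if there are this many patients achieving OR". The Statistical Considerations part of the abstract repeats all of this.

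The toxicity rule in the same section pools both cohorts, and its action is "we will stop the trial for new patient enrollment if at any time during the study we determine" that the toxicity criterion is met. There the term can only mean the whole study: Table 14.5 runs to 42 patients and Table 14.6 gives average sizes up to 47.9.

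No section says what happens to one cohort when the other meets its futility boundary.

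**The concern.** One term serves for closing the whole study (toxicity) and, apparently, for closing half of it (futility). Someone applying the futility text and table headers as they stand would close a cohort that has not met its own boundary.

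The cohorts are different populations, relapsed or refractory against untreated, with different thresholds. Cohort 2's threshold is demanding: Table 14.4 shows it stopping with probability 0.78 at 30%, the rate the plan gives for rituximab alone. Read literally, that outcome would also end enrolment of relapsed or refractory patients, even if they were responding well above their own target. In the other direction, inactivity in cohort 1 would end cohort 2.

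A stopping rule for the primary endpoint should be executable without interpretation. This matters more here because the abstract names no data safety monitoring board and answers no to a schedule of interim analyses. It mentions a monitoring plan, but that plan is not in the documents and cannot be relied on to settle the point.

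**Working it through.** **Inputs (Section 14.0).** Prior Beta(0.6, 1.4) for both cohorts; looks at n = 9, 12, 15, 18 and 21; maximum 24 per cohort; stop when the posterior probability of exceeding the threshold (0.30 for cohort 1, 0.50 for cohort 2) is below 0.05.

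**Step 1: boundaries.** After x responses in n patients the posterior is Beta(0.6 + x, 1.4 + n − x). The largest x with tail probability below 0.05 is the boundary.
- Cohort 1, n = 9: x = 0 gives 0.0096 and x = 1 gives 0.0862, so stop at 0.
- Cohort 2, n = 9: x = 2 gives 0.0305 and x = 3 gives 0.1141, so stop at 0–2.
- Over all looks: 0, 1, 1, 2, 3 (cohort 1) and 2, 3, 4, 5, 7 (cohort 2). These match Tables 14.1 and 14.3.

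**Step 2: the plan's operating characteristics.** An exact binomial recursion over the looks, each cohort run alone, gives:
- Cohort 1, true rate 0.1/0.2/0.3/0.4/0.5: stopping probability 0.876/0.446/0.139/0.030/0.005; average size 13.8/19.4/22.6/23.7/23.9.
- Cohort 2, true rate 0.2/0.3/0.4/0.5/0.6/0.7: stopping probability 0.967/0.775/0.436/0.160/0.037/0.005; average size 11.0/14.8/19.1/22.2/23.5/23.9.

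Tables 14.2 and 14.4 are reproduced, so they describe a design in which each cohort stops only on its own data.

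**Step 3: literal reading, chance that the trial stops for futility.** With independent cohorts and own-data stopping probabilities a (cohort 1) and b (cohort 2), the chance that either boundary is crossed is 1 − (1 − a)(1 − b), whatever the accrual order. With cohort 2 at 50%, b = 0.160:
- cohort 1 at 30%: 1 − 0.861 × 0.840 = 0.277
- cohort 1 at 20%: 1 − 0.554 × 0.840 = 0.53
- cohort 1 at 10%: 1 − 0.124 × 0.840 = 0.896

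**Step 4: literal reading, chance that cohort 2 closes short of 24.** This is the quantity comparable with the 0.16 in Table 14.4. It is b + (1 − b) × Σ s(n) w(n), where s(n) is the chance that cohort 1 stops at look n, and w(n) is the chance that its nth patient enters before cohort 2's 24th. The plan gives no accrual split, so w(n) needs an assumption: each new patient belongs to cohort 1 with a fixed probability (its share of accrual), and outcomes are known at once.

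Worked case: cohort 1 at 30%, share 30%.
- s = 0.0404, 0.0534, 0, 0.0188, 0.0262 at the five looks
- w = 0.656, 0.348, 0.137, 0.041, 0.010
- Σ s(n) w(n) = 0.046
- Result: 0.160 + 0.840 × 0.046 = 0.20

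| Cohort 1 true rate | Either boundary crossed | Cohort 2 short of 24: share 30% | share 50% | share 70% |
|---|---|---|---|---|
| 10% | 0.90 | 0.46 | 0.85 | 0.90 |
| 20% | 0.53 | 0.28 | 0.50 | 0.53 |
| 30% | 0.28 | 0.20 | 0.27 | 0.28 |
| 40% | 0.19 | 0.17 | 0.18 | 0.19 |
| 50% | 0.164 | 0.162 | 0.164 | 0.164 |

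**Step 5: the reverse case.** With cohort 1 at 50% and cohort 2 at 30%, the chance that the trial stops is 1 − (1 − 0.005)(1 − 0.775) = 0.776. Table 14.2 gives 0.005 for cohort 1. By simulation, cohort 2 cuts cohort 1 short of 24 with probability about 0.35 (share 70%), 0.72 (50%) or 0.78 (30%).

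**The case against.** The strongest reply is that the scope is already clear from context. Each paragraph opens with its cohort, Tables 14.1 to 14.4 are each labelled for one cohort, no average size in Tables 14.2 and 14.4 exceeds 24, and where pooling is meant the toxicity text says so. On that view the trial is loose wording for that cohort's enrolment.

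Most of this stands. It is good evidence of intent, and Step 2 adds to it. It does not remove the defect, because the action sentence and the table header are what staff apply at a look, and the same term means the whole study a few lines later.

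Two stronger readings are tempting and are not supported:
- A reader might infer that Tables 14.2 and 14.4 are wrong. They reproduce for cohort-specific stopping, and no figure in them needs changing.
- A reader might set 0.28, 0.53 and 0.90 against the 0.16 in Table 14.4 as cohort 2's own early-stopping probability. Those figures are the chance that either boundary is ever crossed. Cohort 1 may cross after cohort 2 has filled, so the comparable figure depends on an accrual split that the documents do not give.

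It is also fair that the effect is modest when both cohorts are at target. With cohort 1 at 30% and equal accrual, cohort 2's average enrolment falls only from 22.2 to about 20.9. The large figures need cohort 1 to be failing.

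**Conclusion.** The point holds as a wrongly stated action in a primary-endpoint stopping rule, not as a calculation error. The stated action and the stated operating characteristics conflict. The likely intent is cohort-specific stopping, and the tables are correct for it.

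If the wording were followed with cohort 2 at 50%, the chance that cohort 2 closes before 24 patients would rise from 0.16 to about 0.20–0.28, 0.28–0.53 or 0.46–0.90 with cohort 1 at 30%, 20% or 10%. With cohort 1 at 50% it would be about 0.16, essentially unchanged. The ranges assume independent cohorts, immediate outcomes and a cohort 1 accrual share between 30% and 70%. Immediate outcomes is a simplification, since response is assessed over the first 6 months of therapy.

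The documents do not show that anyone meant one cohort's futility to close the other, or that this was done.

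**What to change.** In both futility paragraphs of Section 14.0, and in the matching text of the abstract, replace the instruction to stop the trial with: *enrolment to cohort 1 [cohort 2] will be stopped; the other cohort continues*. Change the headers of Tables 14.1 and 14.3, in both places, to begin *Stop the cohort if*. Keep *stop the trial* only for the pooled toxicity rule and Table 14.5. The action then matches Tables 14.2 and 14.4.

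The cost is wording only: no boundary, table entry, sample size or analysis changes. As the abstract page marks this version as terminated, any report of the trial should also state which reading was applied.
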